6.5 Post-Intervention (between weeks 20-26)

Participants in both arms are asked to complete a post-intervention assessment (between weeks 20-26), which includes:

Post-intervention online questionnaire: Similar items are included on the post-intervention questionnaire as with the baseline and interim assessment with the exception that participants are asked to rate the intervention on multiple dimensions.

Benefits of PA⁵¹

Subjective Norms survey⁵² Social Support for Exercise survey⁵³

Barriers to Exercise survey⁵⁴

Self-Efficacy for Exercise Scale⁵⁵

Patient-Reported Outcomes Measurement Information System⁴⁶⁻⁴⁸

International Physical Activity Questionnaire^{49,50}

Cardiac Anxiety Questionnaire⁵⁶

Changes in Health

Post-Intervention Satisfaction

Physical Activity Stages of Change Questionnaire – Algorithm⁵⁸

Physical Activity Stages of Change Questionnaire - Continuous⁵⁹⁻⁶¹

MVPA and SB: Participants wear an accelerometer again for the same measurement period (7 days) as in previous assessments and complete self-monitoring PA logs in the case they cannot wear the accelerometer (e.g. swimming).

VO_{2max}: VO₂ measurement is obtained again with a graded exercise stress test using a modified Bruce protocol. Participants who were found to have an arrhythmia or show evidence of cardiac ischemia during exercise stress testing will be immediately referred to their cardiologist for follow-up.

Compensation: Participants are compensated \$100 for completion of the post-intervention survey, exercise stress test, and returning the accelerometer with at least 4 days (1 weekend day, 3 weekdays), for at least 10 hours per day of data. Additionally, participants parking and mileage to/from the hospital for the exercise stress test are reimbursed.

6.6 Focus Groups (after post-intervention assessment)

Participants in the intervention arm are asked to partake in a focus group lasting approximately 1.5 hours, to discuss their experiences in the study. There will be 2 groups that meet via videoconferencing with 5-8 participants per group.

Compensation: Participants are compensated \$50 for being in the focus group.

6.7 Additional Incentive

In addition to the compensation described in sections 6.2, 6.4, and 6.5, participants in both arms are able to keep the Fitbit.

7 ASSESSMENT OF SAFETY

7.1 Methods and Timing for Assessing, Recording, and Analyzing Safety Parameters

7.1.1 Adverse Events

Definition

For the current study, an adverse event is an unanticipated change in cardiovascular, musculoskeletal, or emotional symptoms that are (1) concerning to the participant and (2) results in seeking medical attention, if cardiovascular or musculoskeletal in nature. Any condition that is present at the time that the participant is screened will be considered as baseline and not reported as an adverse event. However, if the study participant's condition deteriorates at any time during the study, it will be recorded as an adverse event. Serious adverse events are defined as adverse events that are severe in classification (as described below). We do not anticipate any serious adverse events due to study procedures. Adverse events that occur for participants during the course of the study are comprehensively documented, including events during the stress test, symptoms reported during the course of the intervention from participants in the intervention arm, dates and reasons for pauses in the study protocol due to symptom reporting, and determination of ability to proceed by participants' cardiologists. All unscheduled cardiology outpatient visits, visits to urgent care or the emergency department, unscheduled hospitalizations, or any other changes in health are documented. Participants in the comparison arm are asked whether they sought medical attention in the aforementioned contexts during the interim and post-intervention questionnaires. Additionally, the occurrence of any adverse event or serious adverse event may come to the attention of study staff during other study contacts (e.g., intervention meetings).

Classification

All adverse events and serious adverse events will be assessed by the PI and the study physician, [name], according to the guidelines outlined here.

Severity: The following guidelines will be used to describe severity:

- Mild: Events require minimal or no treatment and do not interfere with the participant's daily activities.
- Moderate: Events result in a low level of inconvenience or concern with the therapeutic measures. Moderate events may cause some interference with functioning.
- Severe: Events that require in-patient hospitalization and/or resulted in death or permanent disability.

Relationship to Study Intervention: The degree of certainty about causality will be graded using the categories below.

- Related: The adverse event is known to occur with the study procedures, there is a reasonable possibility that the study procedures caused the adverse event, or there is a temporal relationship between the study procedures and the adverse event. Reasonable possibility means that there is evidence to suggest a causal relationship between the study procedures and the adverse event.
- Not Related: There is not a reasonable possibility that the study procedures caused the adverse event, there is no temporal relationship between the study procedures and adverse event onset, or an alternate etiology has been established.

Expectedness: It is determined whether an adverse event is expected or unexpected, according to the following criteria.

- Expected: Adverse event is consistent with the risk information previously described for the study procedures.
- Unexpected: Adverse event is not consistent with the risk information previously described for the study procedures.

Safety Procedures

The current study has several procedures in place to reduce the likelihood of serious medical adverse events. Potential participants' cardiologists are notified prior to being recruited for the study and excluded if the cardiologist has communicated or documented any concerns about that young adult engaging in MVPA. All participants undergo a baseline exercise stress test and are not approached for recruitment for Phase 2 if contraindications are detected in Phase 1. In the rare event that a participant has an acute medical event during the exercise stress test, appropriate hospital procedures are enacted, which include calling an emergency response team and immediate evaluation by a cardiologist. The same procedures used for patients undergoing exercise stress testing as part of a medical evaluation are initiated and followed. During the course of the intervention, if a young adult reports cardiac symptoms that are concerning to the participant and are new since the last cardiac evaluation, PA coaches are trained to request that the young adult contact their cardiologist. Young adults have given the study PI, [name], permission to talk with the cardiologist in the instance that a concerning and/or new cardiac symptom is reported. All study procedures are put on hold until the young adult is evaluated by the cardiologist and cleared to proceed with the study.

If a participant was to report bothersome emotional symptoms to study staff during the course of the study, [name], a licensed psychologist, will contact the participant to evaluate the severity of their emotional symptoms. If the participant is not in danger of harming themselves or someone else, [name] will assist the participant in identifying mental health resources. If the participant is positive for significant suicidal or homicidal ideation (i.e., positive for intent, has a plan, and has the means by which to execute a plan), [name] will notify the participant that confidentiality must be broken and the local authorities will be contacted.

7.1.2 Procedures to be Followed in the Event of Abnormal Test Values or Abnormal Clinical Findings

Incidental findings from the exercise stress test are communicated to the participant and the participant's cardiologist. The cardiologist will make a determination as to whether the participant may proceed with the study if an abnormal event, or incidental finding, is detected.

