Similar to the exercise stress test, participants in the intervention arm may experience uncomfortable physical sensations due to exercising, including sore muscles, fatigue, and shortness of breath. If the participant has new cardiac-related symptoms since his/her last cardiology check-up that are concerning to the participant, the interventionist (i.e. PA coaches)

will recommend contacting the participant's cardiologist and the study procedures are put on hold until the cardiologist clears the participant to return to the study. The interventionist also contacts the study PI, [name], who notifies the participant's cardiologist that the participant is experiencing symptoms.

During videoconferencing, PA coaches conduct sessions in privacy and encourage participants to do the same. The same will be encouraged for those who participate in the focus groups. Coaches undergo the same training as other research staff at NCH, including completing Collaborative Institutional Training Initiative (CITI) certification and a day-long instructional seminar on protecting human subjects. Videoconferencing has a lower risk of privacy breach than email communications. Should technical difficulties (e.g., WiFi issues, recorder error) occur during the videoconferencing sessions, PA coaches will make adjustments in accordance with privacy and confidentiality guidelines to conduct the session and/or document the content of the session. These adjustments may include (but are not limited to) conducting the session as a voice call (in the event of videoconferencing issues) or writing a summary of the session (in the event of recorder error). Audio recordings and other documents resulting from these adjustments will be stored on the hospital's secure OneDrive platform. For the purposes of identifying and problem-solving common technical difficulties, PA coaches will record all videoconferencing, recording, and other technical and practical issues. This record will also help identify sessions that may not be available for fidelity evaluation.

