7.1.3 Other Medical Events

Medical events not meeting the above definition of an adverse event.

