7.1.4 Unanticipated Problems

In line with the OHRP definition, unanticipated problems include any incident, experience, or outcome that meets **all** of the following criteria:

1. unexpected (in terms of nature, severity, or frequency) given (a) the research procedures that are described in the protocol-related documents, such as the IRB-approved research protocol and informed consent document; and (b) the characteristics of the subject population being studied;
2. related or possibly related to participation in the research (in this guidance document, *possibly related* means there is a reasonable possibility that the incident, experience, or outcome may have been caused by the procedures involved in the research); and
3. suggests that the research places subjects or others at a greater risk of harm (including physical, psychological, economic, or social harm) than was previously known or recognized.

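### Section 7.1.1 admits only unanticipated changes as adverse events, which conflicts with the later expectedness and relatedness classes and can leave foreseeable events out of the counts

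*Combined protocol and SAP*

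**What the plan says.** Section 7.1.1 (Definition) states that "an adverse event is an unanticipated change in cardiovascular, musculoskeletal, or emotional symptoms". Two further conditions follow: the change must worry the participant, and it must be one that "results in seeking medical attention, if cardiovascular or musculoskeletal in nature". Serious events are nested inside this definition: "Serious adverse events are defined as adverse events that are severe in classification".

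The Classification part of 7.1.1 then has each adverse event assessed for severity, relatedness and expectedness. The Expected class reads "Expected: Adverse event is consistent with the risk information previously described for the study procedures". One route to the Related class is "The adverse event is known to occur with the study procedures".

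Four other places bear on the point:

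- Section 2.3.1 says that intervention-arm participants may have "uncomfortable physical sensations due to exercising, including sore muscles, fatigue, and shortness of breath". It also accepts that learning of an abnormal stress test could be distressing.
- Section 7.1.3 consists of one line: "Medical events not meeting the above definition of an adverse event".
- Section 7.2.1 sends adverse events to the DSMB at each meeting and to the IRB annually.
- Sections 7.2.2 and 7.4 use *unexpected* to pick out the serious events that need prompt reporting or an ad hoc meeting.

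**The concern.** An adverse event definition normally decides what is counted, and expectedness is judged afterwards. Here the entry condition already asks whether the change was foreseen. An event that matches the described risks may be turned away before anyone grades it, although the later classes are written as if such events had been admitted.

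At stake is what the DSMB and IRB see. Foreseeable effects of exercise are among the events that a pilot of an activity intervention should tabulate before a larger trial. If one staff member takes the word literally and another ignores it, the same event is counted or not according to who reads the definition.

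**Working it through.** The documents give no adverse event rate or count, so there is no figure to reproduce. The check sets the provisions side by side.

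**1. Entry against classification.** Entry requires *unanticipated*. Expected means consistent with the risks already described. A new event that was anticipated because it is a described risk fails entry and is never classified. The Related route for events known to occur has the same difficulty. The *unexpected* qualifier in 7.2.2 and 7.4 would add little if every admitted event were already unanticipated.

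**2. Are the two words linked in this protocol?** Section 7.1.4 defines an unanticipated problem as, first, "unexpected (in terms of nature, severity, or frequency) given (a) the research procedures". Section 7.1.1 uses *anticipate* in its ordinary sense when it says that no serious events due to study procedures are foreseen. The literal reading is therefore a natural one, though 7.1.1 does not define the word.

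**3. Which events turn on the word?**

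| New event during the study | Other two conditions | Does *unanticipated* decide? |
|---|---|---|
| Ordinary soreness, no medical visit | Not met | No; excluded anyway |
| Muscle or exertional symptoms of the 2.3.1 kind, worrying, medical visit | Met | Yes |
| Foreseeable emotional reaction, worrying | Met (no visit needed) | Yes |
| Event of a kind not described in 2.3.1, worrying, medical visit | Met | No; admitted |

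The emotional case is the narrower of the two. Section 7.3 monitors from the start of the Phase 2 intervention to the post-intervention assessment, so distress over a baseline stress test precedes that window.

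**4. Where do the excluded events go?** They go to 7.1.3, which has no content beyond its one line. Grading in 7.1.1 applies to adverse and serious adverse events. Reporting in 7.2 covers those two classes and unanticipated problems. The last class also requires the event to be unexpected, so it does not recover foreseeable ones.

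**5. What is still captured?** Section 7.1.1 records deterioration of a condition present at screening as an adverse event, without repeating *unanticipated*. It also documents unscheduled visits, hospitalizations and other health changes. Section 7.5 gives the DSMB separate counts of stress-test abnormalities and of treatment-arm participants who contacted their cardiologist about symptoms. Those counts would not show a musculoskeletal or emotional event, and documentation alone brings no severity, relatedness or expectedness grade.

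**6. Size.** The omission runs from none of the events marked Yes in step 3, if all staff read the word loosely, to all of them, if all read it literally. Their number cannot be estimated from the documents.

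**The case against.** The best defence is that the word is undefined and can be read as not foreseen for that participant, which would give effect to both the definition and the Expected class. Section 7.1.1 also lists symptoms reported during the intervention among the adverse events that are documented. This stands as evidence of ambiguity. It does not remove the conflict: if the loose reading was meant, the word does no work.

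Several stronger readings are tempting, and the documents do not support them:

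- A reader might infer that no event can ever be Expected. The deterioration sentence admits worsening of a baseline condition, and every participant enters with moderate or complex disease. Section 2.3.1 also describes discomfort with survey items while calling it not anticipated, so an event can be both described and unanticipated.
- A reader might infer that every medically attended muscle or breathing complaint is lost. Section 7.1.4 lets severity or frequency make an event unexpected, so a symptom bad enough to prompt a visit could be judged unanticipated. The exertional list in 2.3.1 is also short.
- A reader might infer that serious events drop out, since they are nested in adverse events. Section 7.1.1 says that none due to study procedures is anticipated, so such an event passes the entry condition.
- A reader might infer a bias between arms towards no harm, because 2.3.1 ties the exertional symptoms to the intervention arm. Section 7.8 plans no between-arm safety comparison, and both arms receive an exercise prescription. Detection is unequal the other way: the coached arm has eight sessions in which symptoms can surface, while comparison participants are asked at two questionnaires. No net direction can be derived.
- A reader might infer that the harms go unrecorded. They are documented; what may be missing is their place in the graded and reported counts.

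**Conclusion.** The definition in 7.1.1 is inconsistent with the classification that follows it and sits badly with 7.2.2 and 7.4. On a literal reading, new events that are foreseeable and otherwise meet the definition are left ungraded and outside the adverse event reports. The affected set is limited to medically attended cardiovascular or musculoskeletal events and to emotional events.

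The conclusion assumes that at least some staff equate *unanticipated* with not being a described risk, as the wording of 7.1.4 encourages. The extent of any undercount is unknown. The point should be corrected because a stated rule is wrong as written and decides what oversight bodies receive; it does not show that the safety data will be misleading overall.

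**What to change.** Delete *unanticipated* from the definition in 7.1.1. Keep the other two conditions as they are: the change worries the participant, and medical attention is sought if it is cardiovascular or musculoskeletal. Judge expectedness only at the classification step, against the risks described in the protocol. Sections 7.1.1, 7.2.2 and 7.4 then agree without further edits. Any events already documented but left ungraded can be re-read against the amended definition, so that the counts rest on one rule.

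The cost is one word, the IRB approval that 10.2 requires for any amendment, and a few more events to grade and report. The underlying information is already documented under 7.1.1, and participants' assessments do not change.

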7.2.2 Serious Adverse Events

The DSMB is notified of any serious adverse events determined to be related to the intervention and are unexpected within 5 business days of discovery. Other serious adverse events are reported to the DSMB at each meeting.

Similarly, and per the NCH HRP-103 (updated 12/10/2018), serious adverse events determined to be related to the intervention and are unexpected are reported to the NCH IRB within 5 business days of discovery. Other serious adverse events are reported to the NCH IRB annually.

Serious adverse events that are fatal or life-threatening and are unexpected are reported to NHLBI within 7 calendar days of discovery by the investigator. For non-fatal, non-life-threatening unexpected, serious adverse events, NHLBI is notified within 15 calendar days, by the investigator.

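### The serious adverse event definition in 7.1.1 omits life-threatening events, so an unexpected one that does not require hospitalization misses the expedited clocks in 7.2.2

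*Combined protocol and SAP*

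**What the plan says.** All references are to the combined protocol and SAP.

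- **Definition of serious (7.1.1).** There is one route: "Serious adverse events are defined as adverse events that are severe in classification". No other criterion for seriousness is given.
- **Grades (7.1.1).** The top grade reads "Severe: Events that require in-patient hospitalization and/or resulted in death or permanent disability". The grade below it describes limited inconvenience or concern and adds that "Moderate events may cause some interference with functioning". No grade mentions a threat to life.
- **NHLBI clocks (7.2.2).** "Serious adverse events that are fatal or life-threatening and are unexpected are reported to NHLBI within 7 calendar days of discovery by the investigator". For the remainder, "For non-fatal, non-life-threatening unexpected, serious adverse events, NHLBI is notified within 15 calendar days, by the investigator".
- **DSMB and IRB clocks (7.2.2).** "The DSMB is notified of any serious adverse events determined to be related to the intervention and are unexpected within 5 business days of discovery". The IRB has the same limit under the same two conditions. Other serious events go to the DSMB at each meeting and to the IRB annually.
- **Halting meeting (7.4).** An ad hoc meeting is called when an unexpected serious adverse event is found to be related to the intervention.
- **Events that are not serious.** Under 7.2.1 they go to the DSMB at each meeting and to the IRB annually. Under 7.2.3, one that is an unanticipated problem goes to the DSMB within 2 weeks and to NHLBI within 14 days. Section 7.1.4 requires three things for that status: the event is unexpected, it is at least possibly related to the research, and it suggests greater risk than was known.

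**The concern.** Section 7.2.2 treats life-threatening events as belonging with deaths in its most urgent tier. The definition that decides whether an event can enter that tier does not list them. The 7-day rule applies to events that are already serious, so it cannot itself bring a life-threatening event in.

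The protocol foresees the setting in which this matters. Its safety procedures in 7.1.1 provide for an acute event during a stress test, with an emergency response team and immediate evaluation by a cardiologist. The same section lists emergency department visits separately from unscheduled hospitalizations. An event that threatens life but is resolved in the clinic or emergency department, with no need for admission, falls between the two sections.

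Serious status controls the expedited notices in 7.2.2 and the event-based trigger in 7.4. With 40 participants planned for the randomized phase, a single misclassified event could be the whole safety signal.

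**Working it through.** There is no figure in the plan to reproduce. The check follows an event through the definitions, from adverse event to grade, serious status, reporting clock and halting meeting.

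**Step 1. Classify the event.** Take an event that counts as an adverse event under 7.1.1, threatens life, does not require in-patient hospitalization, and causes neither death nor permanent disability. It meets none of the conditions for the severe grade, so under 7.1.1 it is not serious. The moderate grade describes it poorly, but no other route to seriousness is written.

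**Step 2. Apply the reporting rules**, as written and with life-threatening added to the definition.

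| Event from step 1 | As written | With the addition |
|---|---|---|
| Unexpected, related, suggests greater risk than known | Unanticipated problem: DSMB 2 weeks, NHLBI 14 days; no 7.4 meeting | NHLBI 7 days; DSMB and IRB 5 business days; 7.4 meeting |
| Unexpected, related, not judged to suggest greater risk | DSMB at next meeting; IRB annually | NHLBI 7 days; DSMB and IRB 5 business days; 7.4 meeting |
| Unexpected, unrelated | DSMB at next meeting; IRB annually | NHLBI 7 days; DSMB and IRB unchanged |
| Expected | DSMB at next meeting; IRB annually | No expedited clock; timing unchanged |

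In the table, related means related to the intervention, as 7.2.2 and 7.4 require. A life-threatening event that does require hospitalization is already serious, and nothing changes for it.

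**Step 3. Size the delay.**

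- *First row, NHLBI:* 14 − 7 = 7 more calendar days, and 14 / 7 = 2 times the limit.
- *First row, DSMB:* 2 weeks × 5 business days = 10 business days against 5, again twice the limit (ignoring holidays).
- *Second and third rows:* as written there is no fixed limit, only the next DSMB meeting and the annual IRB report. Section 7.2.1 names no report to NHLBI.

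**Step 4. Look for a repair elsewhere.** No other section defines life-threatening or adds it to the serious definition. Section 7.2.3 softens the consequence for some events but does not make them serious.

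**The case against.** The strongest reply is that the gap is small and partly covered. Most of that reply stands.

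- **The unanticipated-problem route exists.** A reader might infer that such an event simply waits for the next routine report, perhaps about six months if the bi-yearly reports in 7.5 are twice a year. The documents do not support that in general. An event that is unexpected, related and life-threatening would very plausibly also suggest greater risk, and then 7.2.3 applies. The route is still slower, needs all three criteria, and does not start 7.4.
- **Unexpectedness is required throughout.** Every expedited clock in 7.2.2, and 7.4, needs it; the DSMB/IRB clock and 7.4 also need relatedness. A reader might infer that every life-threatening event without admission is lost from expedited reporting. That is too broad. An exercise-induced arrhythmia, which 2.3.1 and 5.2 already name as something the stress test looks for, could be judged expected. No clock would then start under either wording.
- **Need for hospitalization, not admission itself, is the test.** Many life-threatening events will be judged to require it and are already serious. So 7.2.2 is not inoperative; the definition behind it is incomplete.
- **Exposure cannot be read off the stress tests.** It is tempting to add up to 90 baseline and up to 40 follow-up tests. But 7.3 starts adverse event monitoring with the Phase 2 intervention, although 7.1.1 does document stress-test events, and section 14 allows some follow-up tests to be dropped. A count of tests is in any case not a count of events.
- **Immediate care does not depend on the label.** Emergency response, cardiologist evaluation and the cardiology team's decision on continuing apply regardless. The point concerns notification and the formal review only.

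One could add that the grades are called guidelines, so sensible assessors would call such an event severe. They might, but only by departing from the written criteria.

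**Conclusion.** The point holds as a narrow inconsistency between 7.1.1 and 7.2.2. It affects unexpected life-threatening events that do not require hospitalization and cause no death or permanent disability. Those that are unanticipated problems reach NHLBI and the DSMB at about twice the expedited limit and bypass the halting meeting. The others are reported only routinely, although 7.2.2 evidently means unexpected life-threatening events to reach NHLBI within 7 days whether or not they are related.

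This rests on reading 7.1.1 literally and on the event meeting the protocol's adverse event definition in the first place. The documents give no frequency for such events, so the number affected cannot be estimated.

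**What to change.** Reconcile 7.1.1 with 7.2.2 by adding life-threatening to the severe/serious definition in 7.1.1, and make the same change on the event form. The definition then covers every category for which 7.2.2 sets a clock. The clocks, the halting rule and clinical management need no change.

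The cost is one phrase in the protocol, the matching entry on the form, and possibly one or two more expedited reports. That number is a judgement, since the documents supply no event rate.
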